Phase II Randomized Study of Lower Doses of Decitabine (DAC; 20 mg/m² IV daily for 3 days every month) versus Azacitidine (AZA; 75 mg/m² SC/IV daily for 3 days every month) versus Azacitidine (AZA; 75 mg/m² SC/IV daily for 5 days every month) in MDS Patients with Low and Intermediate-1 Risk Disease Transfusion-Dependent versus Best Supportive Care (BSC) in MDS Patients with Low and Intermediate-1 Risk Disease Transfusion-Independent

Study Chair

[name]
The University of Texas M.D. Anderson Cancer Center
[name]
[name]
[contact]
[contact]

Co-Chair

[name]
The University of Texas M.D. Anderson Cancer Center
[name]
[name]
[contact]
[contact]
[contact]

I. OBJECTIVES

Primary:

Compare the event-free survival rates of two different drugs: DAC versus AZA on an abbreviated schedule to a standard arm of AZA given over 5 days in patients with low-risk MDS transfusion-dependent and to BSC in patients with low-risk MDS transfusion-independent.

Secondary:

Compare the response rates for the transfusion independent and the transfusion dependent patients. For example the response rate of two different drugs DAC versus AZA on abbreviated schedule to a standard arm of AZA given over 5 days.

Evaluate the durability of response, the overall and transformation-free survival rates, and the safety profile of 2 different drugs.

The quality of life protocol (2014-0636) titled “Interventional Validation of an MDS-Specific Measure of Quality of Life: Assessing the Responsiveness of the QUALMS-1 to Different Hypomethylating Agent Regimens for Low and Intermediate Risk Disease” was written specifically as a companion study to protocol 2014-0112 and may be offered as an optional assessment to patients enrolled onto this protocol.

II. RATIONALE

Myelodysplastic syndromes (MDS) are clonal hematopoietic stem-cell disorders characterized by ineffective hematopoiesis, peripheral-blood cytopenias, and increased tendency to progress to acute myeloid leukemia (AML).¹ Median age of patients with MDS is approximately 70 years.² This patient population is frequently affected by other comorbid conditions, a factor that often influences treatment decisions.

Treatment of MDS is based on prognostic factors that predict survival and progression to AML. The most widely used prognostic system for therapeutic decision making is still

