This is an adaptive randomized phase II trial for low-risk MDS patients. Regarding the patients transfusion status, patients can be categorized as transfusion dependent and transfusion independent patients. It is expected that there will be half of the transfusion-dependent patients and half of transfusion-independent patients. For transfusion dependent patients, the goal is to compare three treatment arms: 1) DAC, 2) AZA3 (treatment of 3 days), and 3) AZA5 (treatment of 5 days). For transfusion independent patients, the goal is to compare four treatment arms: 1) best supportive care (BSC) 2) DAC, 3) AZA3 (treatment of 3 days), and 4) AZA5 (treatment of 5 days). The primary outcome is event free survival (EFS) defined as the time from beginning of treatment till an event occurs or last follow-up. For transfusion independent patients, the events includes lack of response, requirement of blood transfusion, progression to advanced stages of disease, transformation into AML, discontinuation of therapy due to side effects, and death. The patients who change from transfusion independence to transfusion dependence under BSC will be enrolled in transfusion-dependent group and adaptively assign to the three treatment arms, that is, DAC, AZA3, or AZA5. For transfusion dependent patients, the events includes lack of response, progression to advanced stages of disease, transformation into AML, discontinuation of therapy due to side effects, and death.

Study design

The maximum number of patients accrued will be 240. There will be two parallel adaptive randomization trials for transfusion dependent (N=120) and transfusion independent (N=120) patients respectively. Since we are expecting patients under BSC

will eventually become the transfusion dependent, it is assumed that initially there will be 120 patients under transfusion-dependent group, and the total number increases to about 150 after enrolling the approximate 30 patients under BSC.

Part I Transfusion dependent patients (N=150)

Design

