Patients will be randomized using a Bayesian adaptive algorithm. Patients will be randomized fairly among the three arms at the start of the trial (for the first 30 patients), that is, 10 patients per arm. Thereafter, as the trial progresses and data accrue, the randomization will become unbalanced in favor of the treatment that, on average, has better results in terms of event free survival. Therefore, each successive patient is more likely to receive the treatment with better results, on average. A minimum of 30 and a maximum of 150 patients will be accrued. There will be 12 months follow up after the last patient is accrued with an anticipated accrual rate of 5 patients per month.

Denote the event free survival for the patients in the three arms (DAC; AZA3; AZA5) as T_i for $i=1,2,3$. Assume the T_i is independent exponential with median μ_i . And each μ_i independently follows an inverse gamma distribution with parameter $\alpha=2.05$, $\beta=7.34$. The parameters were chosen to set the mean of the prior equal to 7 (the historical median EFS in months) and a variance of 1000. For each patient, the randomization probability for treatment arm i will be based on the posterior probability that it has the largest median EFS. For example, for arm 1, the posterior probability is $\pi_1=\Pr(\mu_1 > \mu_i)$ for $i=2,3$. In order to avoid aggressively favoring one arm too early in a large trial, instead of

assigning patients with posterior probability, we use its square root transformation as in the following formula to assign patients:

$$Aa = \frac{\sqrt{\pi_1}}{\sqrt{\pi_1} + \sqrt{\pi_2} + \sqrt{\pi_3}}, \text{ where } Aa \text{ is the probability of assigning patients to arm 1, } \pi_1 \text{ is}$$

the posterior probability that arm 1 is superior, etc.

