Table 5: Operating characteristics of safety monitoring

True Toxicity Rate	Prob (stop the trial early)
0.15	0.04
0.2	0.25
0.25	0.68
0.3	0.94

Part II: Transfusion independent patients (N=120)

Design

Patients will be randomized using a Bayesian adaptive algorithm. Patients will be randomized fairly among the four arms at the start of the trial (for the first 40 patients), that is, 10 patients per arm. Thereafter, as the trial progresses and data accrue, the randomization will become unbalanced in favor of the treatment that, on average, has better results in terms of event free survival. Therefore, each successive patient is more likely to receive the treatment with better results, on average. A minimum of 40 and a maximum of 120 patients will be accrued. There will be 12 months follow up after the last patient is accrued with an anticipated accrual rate of 4 patients per month.

Denote the event free survival for the patients in the four arms (BSC; DAC; AZA3; AZA5) as T_i for $i=1,2,3,4$. Assume the T_i is independent exponential with median μ_i . And each μ_i independently follows an inverse gamma distribution with parameter $\alpha=2.14$, $\beta=13.73$. The parameters were chosen to set the mean of the prior equal to 12 (the historical median EFS in months) and a variance of 1000. For each patient, the randomization probability for treatment arm i will be based on the posterior probability that it has the largest median EFS. For example, for arm 1, the posterior probability is $\pi_1=\Pr(\mu_1 > \mu_i)$ for $i=2,3,4$. In order to avoid favoring one arm earlier in a large trial, instead of assigning patients with posterior probability, we use the following formula to assign patients:

$Aa = \frac{\sqrt{\pi_1}}{\sqrt{\pi_1} + \sqrt{\pi_2} + \sqrt{\pi_3} + \sqrt{\pi_4}}$, where Aa is the probability of assigning patients to arm 1, π_1 is the posterior probability that arm 1 is superior, etc.

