If at any point during the trial $\Pr(\mu_i > \max(u_j \text{ for all } j \neq i) | \text{data}) > 0.975$ (< 0.025), the trial will be terminated and treatment i will be selected as superior (inferior). If the maximum accrual is reached and $\Pr(\mu_i > \max\{u_j \text{ for all } j \neq i\} | \text{data}) > 0.8$ (< 0.2), treatment i will be selected as superior (inferior). A treatment arm will be dropped at any point during the trial if $\Pr(\mu_i > 12 | \text{data}) < 0.1$, for $i=1,2,3,4$. Table 6 given below summarizes operating characteristics of the design. The historical median EFS is 12 months. The tables below assume an accrual rate of 4 patients per month. The trial will be stopped early and a treatment selected as being “better” if the probability that one treatment’s median EFS is larger than the other’s EFS exceeds 0.975. If the trial does not stop early and the maximum 120 patients are accrued, a treatment is selected as being “better” if the probability that one treatment’s median EFS is larger than the other’s EFS exceeds 0.8. A treatment arm will be dropped at any point during the trial if the probability that the treatment’s median EFS is larger than 12 months is less than 0.1. The “# of patients treated” row is the average number of patients treated on a given arm under the given scenario. When the medians all equal to 12 months (scenario 1), the probability of selecting one of the three arms (i.e., a false positive result) is at most 3.7 %. The probability of selecting the best treatment (i.e., a true positive result) for scenario 5, when the medians TTP are 12, 12, and 24 months for the arms, respectively, are 0.1%, 0.04%, 0.2%, and 79.7%.

Table 6: simulation results (simulation=5000) for transfusion dependent patients with the minimum randomization probability set as 0.1 and tuning parameter as 0.5

			treatment		
		BSC	DAC	AZA3	AZA5
1	True Median EFS	12	12	12	12
	# of patients treated	29	28.9	28.8	28.6

	Pr(selected)	0.037	0.036	0.034	0.029
	Pr(selected early)	0.001	0.001	0.001	0.0004
	Pr (stopped early)	0.235	0.233	0.253	0.244
2	True Median EFS	7	7	7	7
	# of patients treated	14.2	14.3	14.3	14.4
	Pr(selected)	0.029	0.024	0.027	0.027
	Pr(selected early)	0.0002	0	0.0002	0.0002
	Pr (stopped early)	0.764	0.774	0.773	0.755
3	True Median EFS	7	12	15	20
	# of patients treated	13.2	24.2	32.3	42
	Pr(selected)	0	0.003	0.035	0.496
	Pr(selected early)	0	0.0004	0.003	0.036
	Pr (stopped early)	0.971	0.58	0.296	0.032
4	True Median EFS	12	12	12	20

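### The superiority rule looks only for a single best arm, so a benefit over BSC or AZA5 shared by similar active arms has no decision rule

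*Combined protocol and SAP*

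**What the plan says.** Section I (Objectives, Primary) sets the comparison on event-free survival (EFS) against named references: "to a standard arm of AZA given over 5 days in patients with low-risk MDS transfusion-dependent and to BSC in patients" who are transfusion-independent. Section XII, General Description, is looser. It says "For transfusion independent patients, the goal is to compare four treatment arms" and names no reference contrast.

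The decision rules in section XII, Part I Design and Part II Design, are:

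- **Selection.** If Pr(mu_i > max of all other mu_j | data) exceeds 0.975 during the trial, or 0.8 at maximum accrual, arm i is superior. In both parts an arm below 0.2 at the end is inferior. The wording is "treatment i will be selected as superior (inferior", with the bracketed word for the lower cut. The prose beneath restates the rule as one treatment's median exceeding the other's, which sounds pairwise, but the formula is best-of-all.
- **Dropping.** An arm goes if its probability of exceeding the historical median is too low. In Part II the condition is that the probability that its "median EFS is larger than 12 months is less than 0.1". Part I does the same with 7 months.
- **Below 0.025 during the trial.** Part I suspends accrual to that arm. Part II says the trial is terminated.

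The Analysis Plan adds Kaplan-Meier estimates with 95% credible intervals, a log-rank test and a Cox model. It names no contrast, threshold, error rate or power.

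**The concern.** The objective asks whether treatments differ from AZA5 or from BSC. The superiority rule asks whether one arm stands above all the rest. The two agree when a single arm is clearly best and part company when two or three active arms share a benefit. The Pr(best) values sum to 1. If BSC is near zero and three active arms are equally good, each averages about 1/3, and 0.8 is reached only by chance.

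Similar active arms are plausible here: the Rationale reports response rates of 31% and 36% for the 3-day azacitidine and decitabine schedules. Table 6 nevertheless has no row in which two or more active arms share one benefit over BSC, so the plan does not show how Part II behaves in that case. What is at stake is a trial in which hypomethylating therapy truly beats BSC but the stated rule returns no selection.

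**Working it through.** **Inputs from section XII.** EFS is exponential, with an inverse-gamma prior on each median. Part I uses (2.05, 7.34): mean 7.34/1.05 = 6.99, variance 6.99²/0.05 = 977. Part II uses (2.14, 13.73): mean 13.73/1.14 = 12.04, variance 12.04²/0.14 = 1,036. Both agree with the plan's stated means of 7 and 12 and variance of about 1000. Ten patients per arm are allocated first, then allocation follows the square root of Pr(best) with floor 0.1. The maxima are 150 and 120 patients, accrual is 5 and 4 per month, and follow-up is 12 months after the last patient.

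**Assumptions not in the text.** Poisson arrivals; accrual ends when one undropped arm remains; Pr(best) < 0.025 suspends an arm in Part II as it does in Part I.

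**Plan's own tables.** At most one arm can exceed 0.8, so Pr(selected) adds across arms. The chance of no selection is:

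- Table 3 scenario 5 (7/12/12): 1 − (0.001 + 0.242 + 0.235) = 52.2%
- Table 6 scenario 3 (7/12/15/20): 1 − (0 + 0.003 + 0.035 + 0.496) = 46.6%
- Table 6 scenario 4 (12/12/12/20): 1 − (0.003 + 0.004 + 0.006 + 0.572) = 41.5%
- Table 6 scenario 5 (12/12/12/24): 1 − (0.001 + 0.0004 + 0.002 + 0.797) = 20.0%

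**Reproduction (2,000 trials per scenario).** Pr(AZA5 selected), simulated against stated: Table 6 scenarios 5, 4 and 3, 0.783 v 0.797, 0.557 v 0.572, 0.489 v 0.496; Table 3 scenarios 2 and 4, 0.861 v 0.880, 0.881 v 0.882. All are within 2 points. Two things did not reproduce: early selection (Table 6 scenario 5, 0.235 v 0.059), and the Part I null, which came out at about 0.07 per arm against 0.086-0.098.

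**Shared-benefit cases.** The alternative medians below are assumptions. Ranges are the spread over separate runs of 500 to 2,000 trials per setting. At 600 trials the Monte Carlo SE of a 75% rate is √(0.75 × 0.25/600) = 1.8 points.

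| True medians, months | Some arm selected | At least one Pr(arm > control) > 0.975 |
|---|---|---|
| Part II, BSC 12, active 24/24/24 | 18-20% | about 75% |
| Part II, BSC 12, active 20/20/20 | 18-22% | 55-59% |
| Part II, all 12 | 13.6% (Table 6) | 5-8% |
| Part I, DAC and AZA3 12, AZA5 7 | 45-52% | 72-76% |
| Part I, all 7 | 27.9% (Table 3) | 6-8% |

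The gap does not come from a laxer cut: the control contrast is held to 0.975, while final selection needs only 0.8.

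**Per-arm check by hand.** At 12/24/24/24 the simulated trials average about 16 BSC patients with 13.3 events, and about 17.5 events per active arm. SE(log ratio) = √(1/13.3 + 1/17.5) = 0.364; z = ln 2/0.364 = 1.91; power = Φ(1.91 − 1.96) ≈ 0.48. Simulation gives 48-51%. At 12/20/20/20, with 14.8 and about 19.3 events, SE = 0.346, z = 0.511/0.346 = 1.48, power ≈ 0.32, against a simulated 33-34%.

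**The inferior limb.** With four equal arms each Pr(best) averages 0.25, only just above the 0.2 cut. BSC ends below 0.2 in 99.6% of trials at 12/24/24/24, but also in about 54% when all four medians are 12. At 12/24/24/24 each equally effective active arm is below 0.2 in about 40%.

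**The case against.** **Not naming a winner among equals is proper behaviour for a phase II selection design.** This stands, and best-arm selection should not be changed. It does not supply an answer to the objective, which asks about a control.

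**With one clearly best arm the rule does the job.** This also stands. Pr(selected) for that arm is 0.757 to 0.883 in Table 3 scenarios 2, 4, 6 and 7 and 0.797 in Table 6 scenario 5, though 0.572 in Table 6 scenario 4. An active arm selected as best has, by the same posterior, also beaten the control. A reader might infer that the design usually cannot answer its primary question; these rows do not support that.

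**Other rules and analyses exist.** A reader might infer that such a trial reports nothing. It would not: the Analysis Plan yields EFS by arm, a log-rank test and a Cox model, from which the contrasts can be drawn. What is missing is a stated contrast and threshold. The drop rule compares an arm with history rather than with BSC, and the inferior limb is not specific.

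**Table 3 scenario 5 is not an example of missed superiority over control.** It is tempting to cite its 52% that way. But AZA5, the standard, is one of the two good arms at 12 months; declining to separate it from AZA3 is right, and DAC is stopped early in 0.877. A contrast with AZA5 would rarely fire there (about 4% in simulation).

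**Part II read literally terminates the trial when an arm falls below 0.025.** On that reading about 69% of trials at 12/24/24/24 end with BSC called inferior, with a mean of 56 patients, but so do about 22% when all medians are 12. Table 6 scenario 3 fits suspension: BSC is stopped early in 0.971, yet the arms total 13.2 + 24.2 + 32.3 + 42 = 111.7 patients. The passages conflict, and the figures here depend on the reading chosen.

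**Conclusion.** The concern holds for the case of similar active arms. Superiority is decided only on Pr(best of all), while the primary objective names AZA5 and BSC as comparators, and no stated rule decides those contrasts. If all three active arms share a 12-to-24-month gain over BSC, the rule selects an arm in about one trial in five, against about three in four with at least one convincing contrast with BSC. In Part I, with AZA5 at 7 and both 3-day arms at 12, the corresponding figures are about 45-52% and 72-76%.

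The three-in-four figure is for any of three arms. Per arm the chance is only about a half, because adaptive allocation leaves about 16-17 patients on BSC. The results rest on assumed medians beyond the tabulated scenarios, exponential EFS, and suspension rather than termination in Part II.

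**What to change.** At the final analysis:

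- In Part II, add Pr(mu_active > mu_BSC) for each active arm. In Part I, add Pr(mu_DAC > mu_AZA5) and Pr(mu_AZA3 > mu_AZA5).
- Declare superiority to control above 0.975, and report the posterior of each contrast in both directions so that a 3-day arm doing worse than AZA5 is also visible.
- State the simulated null rate for any such claim (about 5-8% here) and the per-arm power.
- Add shared-benefit rows, such as 12/24/24/24, to Table 6.
- Reconcile the Part I and Part II statements of what follows when Pr(best) falls below 0.025, and rerun the simulations under the reconciled text.

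Allocation, dropping and best-arm selection stay unchanged. The cost is a few posterior summaries from data already held and one further set of simulations. The downside is a small extra false-positive rate on top of the existing null selection rates (27.9% for any arm in Table 3 scenario 1, 13.6% in Table 6 scenario 1), which should be stated.

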Appendix A

Appendix Subtitle:

Leukemia-specific Adverse Event Recording and Reporting Guidelines

These guidelines serve to bring the Department of Leukemia in compliance with the institutional policy on Reporting of Serious Adverse Events-definition of expected AE- "All clinical protocols should include a list of the expected and anticipated events or hospitalizations relating to the study treatment" and Guideline for Good Clinical Practice 4.11.1 "All serious adverse events (SAEs) should be reported immediately to the sponsor except for those SAEs that the protocol or other document (e.g., Investigator's Brochure) identifies as not needing immediate reporting".

Adverse event is any untoward medical occurrence that may present during treatment with a pharmaceutical product but which does not necessarily have a causal relationship with this treatment.

Adverse drug reaction is a response to a drug which is noxious and unintended and which occurs at doses normally used in man for prophylaxis, diagnosis, or therapy of disease or for the modification of physiologic function.

Assessing causal connections between agents and disease is fundamental to the understanding of adverse drug reactions. In general, a drug may be considered a contributory cause of an adverse event if, had the drug not been administered, 1) the event would not have happened at all, 2) the event would have occurred later than it actually did, or 3) the event would have been less severe.

Adverse Events (AEs) will be evaluated according to current CTC version in each protocol. Only unexpected AEs will be recorded in the Case Report Form (CRF).

Expected events during leukemia therapy are:

1. *Myelosuppression related events (due to disease or leukemia therapy)*
 - a. *febrile or infection episodes not requiring management in the intensive care unit*
 - b. *epistaxis or bleeding except for catastrophic CNS or pulmonary hemorrhage*
 - c. *anemia, neutropenia, lymphopenia, thrombocytopenia, leukopenia, leukocytosis*
2. *Disease related events*
 - a. *symptoms associated with anemia*
 - i. *fatigue*
 - ii. *weakness*
 - iii. *shortness of breath*
 - b. *electrolyte abnormalities (sodium, potassium, bicarbonate, CO₂, magnesium)*
 - c. *chemistry abnormalities (LDH, phosphorus, calcium, BUN, protein, albumin, uric acid, alkaline phosphatase, glucose)*
 - d. *coagulation abnormalities*
 - e. *disease specific therapy (induction, maintenance, salvage, or stem cell therapy)*

- f. alopecia
 - g. bone, joint, or muscle pain
 - h. liver function test abnormalities associated with infection or disease progression
 - i. disease progression
- 3. General therapy related events
 - a. catheter related events
 - b. renal failure related to tumor lysis syndrome or antibiotic/antifungal therapy
 - c. rash related to antibiotic use
- 4. **Hospitalization for the management of any of the above expected events**

Abnormal hematologic values will not be recorded on the CRF. For abnormal chemical values grade 3 or 4, the apotheosis will be reported per course in the CRF.

Serious Adverse Event Reporting (SAE)

A serious adverse event (experience) or reaction is any untoward medical occurrence that at any dose

- Results in death
- Is life-threatening
- Requires inpatient hospitalization or prolongation of existing hospitalization
- Results in persistent or significant disability/incapacity
- A congenital anomaly/birth defect.

Important medical events that may not result in death, be life-threatening, or require hospitalization may be considered a serious adverse drug experience when, based upon appropriate medical judgment, they may jeopardize the patient or subject and may require medical or surgical intervention to prevent one of the outcomes listed in this definition. Examples of such medical events include allergic bronchospasm requiring intensive treatment in an emergency room or at home, blood dyscrasias or convulsions that do not result in inpatient hospitalization, or the development of drug dependency or drug abuse (21 CFR 312.32).

(Sections relating to ORERM are for MDACC held IND studies only.)

Important medical events as defined above may also be considered serious adverse events. Any important medical event can and should be reported to the IRB as an SAE if deemed appropriate by the Principal Investigator, the IND Sponsor, or the Office of Research Education and Regulatory Management (ORERM).

All events occurring during the conduct of a protocol and meeting the definition of a SAE must be reported to the IRB in accordance with the timeframes and procedures outlined in "University of Texas M. D. Anderson Cancer Center Institutional Review Board Policy on Reporting Serious Adverse Events". Unless stated otherwise in the protocol, all SAEs, expected or unexpected, must be reported to ORERM, regardless of attribution (within 5 working days of knowledge of the event). **Hospitalizations for the management of any expected adverse events (previously described) will not have an**

expedited report but it will be included in the annual report via the SAE log.

All life-threatening or fatal events, expected or unexpected, and regardless of attribution to the study drug, must have a written report submitted within 24 hours (next working day) of knowledge of the event to the Safety Project Manager in ORERM.

The MDACC "Internal SAE Report Form for Prompt Reporting" will be used for reporting to ORERM.

Serious adverse events will be captured from the time the patient signs consent until 30 days after the last dose of drug. Serious adverse events must be followed until clinical recovery is complete and laboratory tests have returned to baseline, progression of the event has stabilized, or there has been acceptable resolution of the event.

Additionally, any serious adverse event that occurs after the 30 day time period that is related to the study treatment must be reported to IRB and ORERM. This may include the development of a secondary malignancy.

Reporting to FDA

Serious adverse events will be forwarded to FDA by the IND Sponsor (Safety Project Manager ORERM) according to 21 CFR 312.32.

It is the responsibility of the PI and the research teams to ensure serious adverse events are reported according to the Code of Federal Regulations, Good Clinical Practices, the protocol guidelines, the sponsor's guidelines, and Institutional Review Board policy.

Reporting of external SAEs

The MDACC institutional policy for reporting of external SAEs will be followed.

Version 1.0/ Sept 09

IRB Approval Date: September 23, 2009

